9.4.3.1. Key Secondary Endpoints

The key secondary endpoints will be analyzed using the Cochrane-Mantel-Haenszel (CMH) test for difference in proportions.

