9.4.4. Other Secondary Endpoints

To compare the proportion of participants with an improvement of at least 1 category relative to Baseline on the 6-point ordinal clinical recovery scale relative to Baseline, the proportion of participants with a worse score relative to Baseline on the 6-point ordinal clinical recovery scale, the proportion of participants who progress to mechanical ventilation (for participants not on mechanical ventilation at baseline), and the mortality rates defined as category 6 on the 6-point ordinal clinical recovery scale, the difference in cumulative incidence at Day 28 will be estimated using the same techniques as for the key secondary endpoints.

Total length of hospitalization, total time on invasive mechanical ventilation, number of ventilation free days, and total time on ECMO will be analyzed by the stratified Wilcoxon Rank-Sum test and using the stratification factors. Corresponding 95% CIs will be derived using the Hodges-Lehmann approach.

Time to improvement of at least 1 category and other ‘time to event’ parameters will be analyzed using the stratified log-rank test.

The distribution of outcomes on the 6-point ordinal clinical recovery scale will be described via plots (eg, stacked bar plots representing the proportion of participants in each category, by treatment arm and over time).

A proportional odds model will be used to analyze the 6-point ordinal clinical recovery scale of the clinical status at Days 7, 14, 21 and 28.

Drugs used in the SOC at baseline and changes in the SOC after treatment administration will be tabulated by treatment group.

The primary and secondary endpoint evaluation will be conducted on the ITT population and on the ITT population restricted to the population with confirmed critical COVID-19 disease. Analyses of qualitative comparison between pre-interim analysis and post-interim analysis for treatment effect in the population with confirmed critical COVID-19 disease will be conducted to check the consistency in the study. This qualitative assessment will be limited to primary and key secondary endpoints only.

Other secondary parameters might be added in the SAP.

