5.3.3 Analysis Method

The data will be analyzed according to the randomized treatment.

For the key secondary endpoints, the CMH analysis for difference in proportions, adjusted for the stratification factors (age [<65 and ≥ 65 years] and use of IMV [yes/no]) will be performed. The comparison between treatment groups will be based on CI-estimates and p-values obtained from this analysis.

A positive value on the common proportion (risk) difference using the Mantel-Haenszel method indicates that the proportion of participants with ‘Sustained clinical improvement at day 28’/‘death by day 28’ is larger in the experimental treatment group. The actual values of the stratification factors will be used, not as randomized.

As a sensitivity analysis, a logistic regression model will be estimated that is adjusted for the treatment group, but also adjusted for additional baseline covariates. The covariates are the following: CRS at baseline (≤ 3 vs > 3), Remdesivir at baseline (yes/no), Glucocorticoids at baseline (yes/no), Number of Comorbidities (0/1/2/ ≥ 3), Sex (Male/Female), Race (Asian/Black or African American/White/Unknown or Not reported), Ethnicity (Hispanic or Latino/Not Hispanic or Latino), Free IL-6 at screening, CRP at screening, ferritin at screening, LDH at screening (high/low/normal) and albumin (low/not low) at screening. Each of the additional baseline covariates will be added to the model to estimate the individual effect of these covariates, after which a stepwise selection method will be applied. A covariate will be added to the model if it is significant at the 25% significance level, while the covariate in the model has to be significant at the 0.15% level for it to remain in the model. In the final logistic regression model the treatment difference in proportions will be estimated. This will be done as follows: in each treatment group the proportion of participants with improvement will be estimated using the average value observed the study (across treatment groups) for both the continues and categorical covariates (based on 0/1 coding for categorical). The delta method will be used for the confidence interval.

Comorbidities considered: Obesity (BMI ≥ 30), Diabetes, Serious Heart Condition/Coronary Heart Disease, Chronic Obstructive Lung Disease, Chronic Kidney Disease and Cancer.

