5.4.2 Analysis Methods

The secondary endpoint evaluation will be conducted on the primary and on the ITT population.

Time-to event parameters

The time-to-event parameters will be evaluated based on the log-rank test, stratified for the stratification factors (age [<65 and ≥ 65 years] and use of IMV [yes/no]). The tests will be performed 1-sided at a 5% significance level. The actual values of the stratification factors will be used, not as randomized.

Cumulative proportion of patients with an event, by treatment, will be provided using the complement of the Kaplan Meier curve. The analyses will be completed with the median time to event (if reached) and the proportion of participants who with an event on day 7, 14, 21 and 28; all per Kaplan Meier method. The complementary log-log transform method is used to calculate the 90% confidence intervals.

Duration parameters

Descriptive statistics of the duration parameters will be shown for all participants that were still alive at day 28.

Total length of hospitalization and number of ventilation free days will be analyzed in the subgroup of participants that were still alive at day 28 by using the Hodges-Lehman approach. Corresponding 90% CIs will be presented as well.

Incidence parameters

For each parameter the number and percentage of participants in each category and subcategory will be tabulated and listed. All participants in the applicable analysis set will be counted for the denominator of the proportion.

The occurrence (yes/no) as described for the incidence parameters will be analyzed using logistic regression as described above (section 5.3).

Proportions: CRS outcome and CRS (As observed) outcome

A tabulation will be made of the CRS and CRS (As observed) outcomes at each day, taking only non-missing values into account (i.e.: the percentages of the six categories per day should sum up to 100%).

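### SAP 5.4.2 makes the stepwise logistic sensitivity model of 5.3.3 the only between-arm analysis of the incidence endpoints; for two of them this contradicts protocol 9.4.4

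*SAP*

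**What the plan says.** **Protocol.** Section 9.4.4 lists improvement of at least one category, worsening, progression to mechanical ventilation, and mortality. For these, "the difference in cumulative incidence at Day 28 will be estimated using the same techniques as for the key secondary endpoints". Section 9.4.3.1 names the technique: "The key secondary endpoints will be analyzed using the Cochrane-Mantel-Haenszel (CMH) test for difference in proportions". That sentence mentions no strata.

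**SAP 5.3.3 (key secondaries).** The main analysis is "the CMH analysis for difference in proportions, adjusted for the stratification factors", namely age group and IMV. As a sensitivity analysis, "a logistic regression model will be estimated that is adjusted for the treatment group" and for further baseline covariates. Twelve candidates are listed; age group and IMV are not among them. Each is tried in the model, "after which a stepwise selection method will be applied". On entry, "A covariate will be added to the model if it is significant at the 25% significance level"; the level for staying in is printed as 0.15%.

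**SAP 5.4.2 (other secondaries).** Counts and percentages are tabulated, and the occurrence "as described for the incidence parameters will be analyzed using logistic regression as described above", with section 5.3 given as the reference. No CMH analysis is mentioned. SAP 5.4.1 labels four endpoints as incidence parameters: one-category improvement, two-category improvement on CRS (As observed), worsening, and ventilation-free survival. SAP 5.1.1 tests the other secondary endpoints at the one-sided 5% level.

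**The concern.** A model that the SAP itself treats as a sensitivity analysis becomes the sole between-arm inference for four endpoints, with no reason given. It has three weaknesses in that role.

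- The covariates are chosen by testing them against the outcome, and the nominal confidence interval does not reflect that choice. The adjustment set can also differ from one endpoint to the next.
- The listed terms leave out both factors used to stratify the randomisation. The Cox sensitivity model in SAP 5.2.3 and the proportional odds model in SAP 5.4.2 both name them.
- The difference in proportions is predicted at average covariate values. With covariates in a logistic model, that is not the stratum-weighted risk difference reported for the key secondaries.

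What is at stake is the reading of the supporting endpoints, and the consistency of the SAP with the protocol.

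**Working it through.** **1. The plan's own figure (context only).** No power is stated for the incidence parameters. For the key secondaries, protocol 9.2 gives at least 80% with 37 control and 74 sirukumab participants at one-sided 5%. The formula is power = Φ[(|p1 − p2| − 1.645·SE0)/SE1], with SE0 pooled and SE1 unpooled.

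- 30% vs 55%: SE0 = 0.1005, SE1 = 0.0950, so Φ(0.893) = 81.4%.
- 40% vs 15%: SE0 = 0.0852, SE1 = 0.0906, so Φ(1.213) = 88.7%.

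The stated figure is reproduced, but these rates do not belong to the endpoints at issue.

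**2. The texts side by side.**

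| Endpoint | Named in protocol 9.4.4 | SAP method | Conflict from this sentence |
|---|---|---|---|
| Improvement of at least 1 category | Yes | Logistic, 5.4.2 | Yes |
| Worsening | Yes | Logistic, 5.4.2 | Yes |
| Progression to ventilation | Yes | Time to event, stratified log-rank | No |
| Mortality | Yes | CMH, 5.3.3 (including the ITT repeat) | No |
| Improvement of at least 2 categories, CRS (As observed) | No | Logistic, 5.4.2 | No |
| Ventilation-free survival | No | Logistic, 5.4.2 | No |

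**3. What the selected model may contain.** The chance that at least one of k independent null covariates meets a stay level a is 1 − (1 − a)^k.

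- k = 12, a = 0.0015 as printed: 1.8%.
- k = 12, a = 0.15, if 15% was meant: 85.8%.
- In the Primary analysis set everyone has baseline CRS 4 or 5 (SAP 2.2.3), so the ≤3 vs >3 covariate is constant and k = 11. The figures become 1.6% and 83.3%.

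As printed, the model will often reduce to treatment alone unless a covariate is strongly prognostic. At 15% it would usually carry at least one noise covariate. These are alternative outcomes, not harms that add up.

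**4. Power if it reduces to treatment alone.** This is a simulation of 4,000 trials per scenario with N = 111, 2:1 blocks within strata, and a one-sided 5% test. The assumed inputs, none of them from the documents, are 40% aged 65 or over, 30% on IMV, and log-odds = −0.25 − b·age − b·IMV + 1.05·treatment (treatment odds ratio e^1.05 = 2.9). Averaged over strata with weights 0.42, 0.46 and 0.12 (neither, one or both factors), the event rates are about 33% vs 57% at b = 0.7 and 28% vs 49% at b = 1.2.

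| Stratum odds ratio, each factor | CMH | Logistic, treatment only | Logistic with strata | CMH minus treatment only |
|---|---|---|---|---|
| e^0.7 = 2.0 | 80.6% | 78.8% | 80.8% | 1.8 points |
| e^1.2 = 3.3 | 77.0% | 72.8% | 77.1% | 4.2 points |

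The Monte Carlo standard error of each power is about 0.6 to 0.7 points. Type I error was 4.6% and 4.9% for CMH, against 4.3% and 4.0% for treatment-only logistic. The stepwise procedure itself was not simulated.

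**The case against.** The strongest reply is that the strata may be intended after all. Footnote 1 to SAP Table 2 asks that inferential models include a baseline CRS flag (≤3 or >3) together with the stratification factor. SAP 5.1.2 says the actual values of the factors are used for all analyses. This has weight: omission of the strata cannot be asserted as certain, and the SAP is better called internally inconsistent. But the footnote uses the singular in a note about IMV and does not clearly cover age. Section 5.1.2 can be read as saying which values to use, rather than which models contain them. Neither passage restores CMH or removes the stepwise selection.

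The consequence is also limited. These endpoints lie outside the testing hierarchy. One-category improvement has a stratified log-rank analysis as well, and Day 28 CRS has a proportional odds model with the strata. That also stands.

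A reader might infer more than the documents support:

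- **That every incidence endpoint departs from the protocol.** Only two do. Protocol 9.4.4 names neither ventilation-free survival nor CRS (As observed), and it allows the SAP to add secondary parameters.
- **That the protocol itself prescribes stratified CMH for these endpoints.** The adjustment for age group and IMV comes from SAP 5.3.3.
- **That the Data Monitoring Committee's worsening criterion is affected.** Protocol 10.4.6 bases it on Fisher's exact test.
- **That leaving out the strata inflates type I error.** In the simulation the treatment-only test was slightly conservative.

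**Conclusion.** The point holds in limited form. For at-least-one-category improvement and for worsening, SAP 5.4.2 departs from protocol 9.4.4 and 9.4.3.1 without explanation. For all four incidence parameters it makes a data-selected sensitivity model the only between-arm inference, and the SAP contradicts itself on whether that model includes the strata.

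The certain costs are intervals that ignore selection and estimates that cannot be set directly beside the key secondaries. The power cost arises only if the model collapses to treatment alone. It is about 2 to 4 points under assumed stratum odds ratios of about 2 to 3.3. The documents give neither event rates for these endpoints nor the prognostic strength of the strata, so this is a range and not an estimate. The SAP should be corrected, but the primary and key secondary conclusions do not depend on it.

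**What to change.** In SAP 5.4.2, replace the logistic sentence with a statement that incidence parameters are analysed by the CMH risk difference adjusted for age group and IMV, as in 5.3.3. In the ITT set, add the baseline CRS flag (≤3 or >3) as a stratifying factor, following footnote 1 to Table 2. Because that footnote equates CRS 5 with IMV use, the flag and IMV together give three levels and not four.

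Keep the logistic model as a sensitivity analysis only, with age group and IMV forced in, and say whether the stay level of 0.15% is intended.

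The cost is a few lines of SAP text before database lock. The CMH analysis is already planned for the key secondaries, and no data collection changes.

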6 VIROLOGY ASSESSMENTS

6.1 General

Analysis of viral load is considered an exploratory analysis.

The virology assessments (copies/mL) will be analysed using ITT and Primary analysis sets.

SARS-CoV-2 viral load will be measured during the study by a qRT-PCR assay on Nasopharyngeal (NP) swabs, endotracheal aspirate (if participant is intubated) and on plasma samples.

6.2 Definitions

Baseline Value: For each of the assays, the baseline value of viral load is defined as the last measurement before the intake of the study drug. If no measurements are available prior to the dose of the study drug, then the first measurement obtained up to and including 60 minutes after the study dose will be considered as the baseline.

6.3 Data Handling Rules

In case there are multiple post-dose viral load measurements on a day for the same assay, then the highest value on that day will be used for the analysis.

All analyses on viral loads from central lab (Covance) will be performed after transforming the non-missing viral load measurements to \log_{10} scale. In the database, the missing values are shown as 'Inconclusive', 'Indeterminate' or 'Not done' and will be excluded from the analysis.

The lower limit of quantification (LLOQ) values for assay on nasopharyngeal (NP) swabs and endotracheal aspirate are 1018 copies/mL, and for plasma samples it is 1660 copies/mL. The measurements below LLOQ may or may not be detectable. If the viral load measurements are below the LLOQ then these are imputed as 1 copy/mL if viral load is undetectable, or as LLOQ/2 if it is detectable.

6.4 Analysis Methods

Two summary tables showing N, mean, SE, median, inter-quartile range, minimum and maximum values over time of (1) viral loads (\log_{10} scale) and (2) change from baseline (change in \log_{10} values) will be generated. Over time tables will use all measurements (planned and unscheduled) for the NP assay at Baseline, Day 3, 7, 10, 14, 21, 28.

To compare the two treatment arms for the viral loads (only for assay of NP) over time 3 plots of viral loads (\log_{10} scale) will be generated: (1) Mean values, (+/- SE), (2) Median/IQ values, and (3) Mean Change from baseline (+/- SE). Over time plots will use all (planned and unscheduled) measurements at Baseline, Day 3, 7, 10, 14, 21, 28.

For each participant, a plot showing viral loads (\log_{10} scale) for Nasopharyngeal swabs, endotracheal aspirate and on plasma samples over time (all scheduled and unscheduled measurements) will be generated. To understand the viral load profiles properly, the LLOQs will be shown by horizontal reference lines. Study days of first onset of COVID-19 symptoms, of

discharge from hospital and of death will be shown by vertical reference lines on each plot. The CRS score at baseline will also be shown on the plot.

6.5 Analysis of Undetectability of Viral Load

For the analysis of undetectability of viral load all subjects with at least a post-baseline measurement of viral load by Nasopharynx assay will be considered.

For the primary analysis, all measurements of viral load up to Day 31 of the study (i.e. protocol window: Day 28+3 days) by the NP assay from central lab (central lab) will be used. Plots for individual participants will be generated using data up to Week 16.

Time (Days) to undetectability of virus load will be evaluated using the **First confirmed undetectability (CU)** approach as described below.

First confirmed undetectability (CU)

A participant is said to have (CU) of viral load if (1) participant has two consecutive undetectable viral loads, or (2) if the last viral load in the database is undetectable.

If there is at least one incidence of the CU then the date of the first undetectability among all CUs will be used to find the days from the study dose date to first CU of viral load. If there is no CU until study Day 31 then participant will be censored at date of last viral load assessment until study Day 31.

Following rules will be applied to derive the flags for event (of first CU) or censoring, and to derive the Days to event or censoring.

[For clarity, in the examples below of different cases a detectable viral load is denoted by 'D', and undetectable by 'U', and 'x' will represent any type of load (undetectable or detectable)].

(1) Case when a participant has only 1 viral load measurement in database (therefore it is also the last viral load measurement):

- a. If the viral load is undetectable then censor flag = No (same as Event = Yes) [example: U => censor flag = No],

Days to event = date of last viral load measurement – dose date + 1.

- b. Otherwise if the viral load is detectable then censor flag = Yes (same as Event = No),
[example: D => censor flag = Yes].

Days to censoring = date of last viral load assessment – dose date + 1.

(2) Case when a participant has more than 1 viral load measurements in the database:

- a. if there are no cases of 'CU cases based on 2 consecutive viral loads' then
 - i. if last viral load in the database is undetectable then

censor flag = No (same as Event = Yes),
 [example: U₁DDU₂DU₃DU₄ => censor flag = No],

ii.if last viral load in the database is detectable then
 censor flag = Yes (same as Event = No),
 [example: U₁DDU₂DU₃D => censor flag = Yes],

In both these cases a(i) and a(ii), the 'Days to event/censoring' will be based on the date of last viral load measurement until study Day 31 in the database.

b. If there are one or more CU cases based on 2 consecutive viral loads then
 censor flag = No (same as Event = Yes),
 and 'Days to event/censoring' will be derived using date of first viral load among the viral loads resulting in CU cases.

[examples: DU₁DU₂U₃D or U₁DU₂U₃U₄DU₅U₆ => censor flag = No,
 and in both cases 'Days to event/censoring' = Days to U₂).]

Summary and Kaplan-Meier Analysis of Time to Undetectability of Viral Load:

The analysis of time-to first CU of viral load is planned by the Kaplan-Meier (KM) analysis. Days to first CU of viral load will also be summarized using the quartiles (and their confidence intervals). The analysis will be performed for ITT and Primary analysis sets. (Note: As per the inclusion criteria of the protocol all participants in the study are detectable for viral load at baseline. Therefore, all participants in the ITT and Primary analysis sets will be included for these analyses, respectively).

For the primary analysis, non-missing planned and unscheduled measurements will be used to generate the summary tables showing n and percentage (cumulative) of participants with CU by Day 3, 7, 10, 14, 21, 28/31. For the final analysis, table will also include Week 16.

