- t. If the participant is intubated, endotracheal samples need to be taken at the same time as the NP swab. If taking both NP and endotracheal samples is not feasible, the NP sample should be given priority.

- u. Lab testing for detection of SARS-CoV-2 on the NP swab at day of hospital discharge. If SARS CoV-2 positive, an additional NP swab will be taken every 7 days, if feasible for the site and tested, until SARS-CoV-2 negative.
- v. If viral RNA is detected in NP samples at day of discharge, all possible efforts will be made to follow-up participants and collect samples every 7 days until viral RNA is negative, considering the current pandemic and related logistical challenges. If possible, home visits by a healthcare professional may be conducted to collect samples during the follow-up period.
- w. Includes serum samples for measurement of PK, antibodies to sirukumab, and IL-6. On Day 1, a predose and a postdose (within 30 minutes after the end of infusion) sample should be collected. The postdose sample should be collected from the arm contralateral to that used for IV infusion. On Day 1 (predose) and Day 28 the PK, antibodies to sirukumab, and IL-6 will be evaluated. On Day 1 (postdose), Day 14, and Day 21 the PK and IL-6 will be evaluated.
- x. PAXgene RNA tubes should always be used last for any blood draw.
- y. An optional pharmacogenetics blood sample (DNA) will be obtained from those participants who gave consent (where local regulations permit).
- z. Sample can be also taken at any other time point after study drug intervention on Day 1.
- aa. For those participants discharged prior to Day 28, all Day 28 assessments should be done at day of discharge. Laboratory, virology, relevant respiratory function related assessments, and biomarker/pharmacology assessments completed maximum 1 day before discharge do not need to be repeated on the day of discharge provided that no clinically relevant changes were noted in the results and the participant was declared 'ready to be discharged' on the day before discharge.
- bb. Assessments done at screening do not need to be repeated at baseline.
- cc. For participants still hospitalized post Day 28, additional blood sampling should be done every 7 days (± 1 day) and at day of discharge.
- dd. For all laboratory tests done on Day 21, Day 28, and every week thereafter as needed, a window of ± 1 day for all sampling is allowed.

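### In the final analysis, SAP 6.5 can count a single late negative swab as viral clearance on a day when virus was still detected

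*SAP*

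**What the plan says.** All of the following is in SAP 6.5 unless noted.

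- **Definition.** Confirmed undetectability (CU) is reached by two undetectable results in a row, or "if the last viral load in the database is undetectable". The general text dates the event from the first undetectable result among the CUs.
- **Flag, case (2)(a)(i).** With several samples and no consecutive pair, the participant is an event "if last viral load in the database is undetectable then". Case (2)(a)(ii) censors when that last sample is detectable. Neither clause has a day limit.
- **Date, cases (2)(a)(i) and (ii).** Days to event or censoring "will be based on the date of last viral load measurement until study Day 31 in the database".
- **Date, case (2)(b).** With a consecutive pair, the time "will be derived using date of first viral load among the viral loads resulting in CU cases". No Day 31 cap is stated.
- **Data window.** "For the primary analysis, all measurements of viral load up to Day 31 of the study" are used (nasopharyngeal assay, central laboratory).
- **Censoring.** "If there is no CU until study Day 31 then participant will be censored" at the last assessment up to that day.
- **Final analysis.** "For the final analysis, table will also include Week 16". SAP Section 1 says that the final analysis uses all available data, follow-up included, with essentially the same methods.

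The protocol plans later samples. Under Section 1.3, footnote u, "If SARS CoV-2 positive, an additional NP swab will be taken every 7 days" after discharge until negative, where feasible for the site. Appendix 3 lists weekly swabs for participants in hospital after Day 28, and swabs at Weeks 8, 12 and 16 under footnote v.

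**The concern.** The flag looks at the last sample ever taken. The date looks at the last sample up to Day 31. When these are different samples, the event can be placed on a day whose own result is detectable.

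Sampling until the first negative tends to produce a run of detectable results and then one undetectable result. That sequence has no consecutive pair, so it falls under case (2)(a)(i), where the two windows differ.

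At stake are the Kaplan-Meier curve, the quartiles and the cumulative clearance table. In the final analysis, a participant who cleared after Day 31 would enter the Day 28/31 column as already cleared. The same participant, censored in the primary analysis, would then become an earlier event although no result up to Day 31 had changed.

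**Working it through.** **Step 1: the plan's own examples.** Writing D for detectable and U for undetectable, the case rules reproduce all six SAP examples: U is an event; D is censored; UDDUDUDU is an event; UDDUDUD is censored; DUDUUD and UDUUUDUU are events at the result that the SAP labels U2. The examples carry no study days, so they do not show which data window is meant.

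**Step 2: sequences with study days.** Samples are on Days 3, 7, 10, 14, 21 and 28 unless stated, then weekly from Day 35. The columns compare the case rules applied to all data, the same rules after a Day 31 cut, and the same rules without the Day 31 date cap.

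| Results | Rules on all data | Data cut at Day 31 first | No Day 31 date cap |
|---|---|---|---|
| D to Day 28, U on 35 | event Day 28 (a D sample) | censored Day 28 | event Day 35 |
| D to Day 35, U on 42 | event Day 28 (a D sample) | censored Day 28 | event Day 42 |
| Positive at discharge on Day 10, D on 17, 24 and 31, U on 38 | event Day 31 (a D sample) | censored Day 31 | event Day 38 |
| D to Day 28, U on 35 and 42 | event Day 35 (a U sample) | censored Day 28 | event Day 35 |
| D to Day 21, U on 28, D on 35, U on 42 | event Day 28 (a U sample) | event Day 28 | event Day 42 |

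The first three rows show the defect. The fourth shows that case (2)(b) is sound. The fifth shows that some (2)(a)(i) events are dated on an isolated undetectable sample.

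**Step 3: how general it is.** I took every possible sequence on this schedule that ends in U after Day 31 and has no consecutive pair:

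- one swab after Day 31: 13 of 13 are dated on a detectable sample;
- two swabs: 13 of 21;
- three swabs: 26 of 34.

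These are counts of sequences, not probabilities. For the run-of-D-then-U pattern, the date always falls on a detectable sample.

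**Step 4: the rules side by side.** For D to Day 28 and U on Day 35 in the final analysis, the section supports three answers:

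- event on Day 35, from the general dating text;
- event on Day 28, from case (2)(a) and its date sentence;
- censored on Day 28, if the sentence censoring anyone without a CU by Day 31 is carried over.

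They cannot all be programmed.

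**Step 5: scale per participant.** SAP 1.4 plans about 74 and 37 participants with critical disease per arm. If all are in the denominator, one such event adds 1/74 = 1.4 points (sirukumab) or 1/37 = 2.7 points (control) to the simple cumulative percentage.

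**The case against.** The best reply is that the primary analysis is already protected. The section limits it to measurements up to Day 31 and censors anyone without a CU by then. If that cut comes first, the last value in the database is the last value up to Day 31, and nobody is misdated. This stands. A reader might infer that the primary analysis is wrong as planned, but the documents do not support that. They support only an ambiguity, which could matter because early enrollees may already have later swabs in the database at that time.

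Three other inferences also go too far:

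- **That the Week 16 column can gain no events.** The cap covers only cases (2)(a)(i) and (ii). Two consecutive late negatives are dated on the first of them.
- **That every participant positive at discharge ends with a negative result.** The protocol makes these swabs depend on site feasibility and logistics, so the pattern is plausible but not assured.
- **That a particular share of participants is affected.** The documents give neither the rate of positivity at discharge nor the completeness of follow-up swabbing.

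It can also be said that the general text already dates a CU from an undetectable result. That is true, but the (2)(a) date sentence is the more specific instruction and contradicts it. Carrying the Day 31 censoring sentence into the final analysis would not rescue the text either, because it would work against adding Week 16 to the table.

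**Conclusion.** The wording is wrong for the final analysis and ambiguous for the primary analysis. In the final analysis, a participant detectable at the last sample up to Day 31, with no earlier consecutive pair and a single later undetectable result as the last one, is an event dated on a detectable sample. This inflates the Day 28/31 percentage and places the event too early on the curve.

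The conclusion assumes that the case rules are programmed as written on all follow-up data, as SAP Section 1 indicates, and that some swabs after Day 31 are obtained. The size is known only per participant (1.4 or 2.7 points at the planned arm sizes).

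The importance is low. SAP 6.1 calls viral load exploratory, no primary or key secondary test depends on it, and individual profiles are plotted to Week 16 in any case.

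**What to change.** Use one data cut for both flag and date in SAP 6.5:

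- **Primary analysis:** set flag and date from the last viral load up to study Day 31.
- **Final analysis:** set the flag from the last viral load up to Week 16. Date a (2)(a)(i) event on that undetectable sample, and censor a (2)(a)(ii) case at the last sample up to Week 16.
- **Consistency:** tie the Day 31 censoring sentence to the primary analysis, apply the same cut to single-sample cases, and add one worked example with study days.

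The Day 28/31 figure may still differ between the two analyses, because a later result can overturn an isolated negative; a table footnote should say so.

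The cost is a few phrases in one section and one cut-off in the derivation program. No new data are needed.
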